### 2.1.1. Primary Estimand(s)

*There are no defined estimands for the incidence of AEs, laboratory abnormalities, changes in vital signs, and ECG findings. These endpoints will be analyzed using Pfizer data standards as applicable. All participants who receive at least 1 dose of IP will be included in the safety analyses. All safety data will be summarized descriptively through appropriate data tabulations, descriptive statistics, categorical summaries, and graphical presentations.*

### 2.1.2. Secondary Estimand(s)

*Two estimands are defined for this study. Estimand 1 (E1) will support specified CDASI assessments at specified timepoints for participants in the Skin Analysis Set and Muscle Analysis Set separately. Estimand 2 (E2) will support TIS and CSM assessments at specified timepoints for participants in the Muscle Analysis Set.*

*E1 will be the population average effect of PF-06823859 on CFB in CDASI activity score at Week 52 for all randomized and dosed participants with non-missing baseline in a specified analysis set (Skin or Muscle Analysis Set) in the absence of dropout. Measurements taken after a participant withdraws from treatment will be censored and treated as missing data. The population-based estimate for the effect of PF-06823859 will be the mean CFB in CDASI-activity score at Week 52.*

*E1 will also be applied to each combination of the following endpoints, timepoints, and analysis sets:*

- Endpoints: Change from baseline and absolute values of CDASI activity score and CDASI damage score;*
- Timepoints: Week 52 and all scheduled intermediate timepoints;*
- Analysis sets: Skin Analysis Set and Muscle Analysis Set.*

*E2 will be the population average estimate for the effect of PF-06823859 on TIS at Week 52 for all randomized and dosed participants with non-missing baseline in the Stage 3 Muscle Analysis Set in the absence of dropouts. Measurements taken after a participant withdraws from treatment will be censored and treated as missing data. The population-based estimate for the effect of PF-06823859 will be the mean TIS at Week 52.*

*E2 will also be applied to each combination of the following endpoints and timepoints in the Stage 3 Analysis Set:*

[figure not shown]
- *Endpoints: TIS and change from baseline in each of the CSM of the TIS.*
- *Timepoints: Week 52 and all scheduled intermediate timepoints.*

## 2.2. Study Design

*This is a Phase 2b, OLE study to evaluate the long-term safety and tolerability of PF-06823859 in adult participants with moderate to severe DM who completed the treatment period of a qualifying study (including Protocol C0251002) and have agreement from their study doctor to continue active treatment. Eligible participants will not have had any significant protocol deviations (eg, not following the protocol, taking prohibited medications, not using appropriate contraception) or have not completed all study treatment in the qualifying study. Approximately 30 participants who complete the Week 24 visit during the treatment period in Study C0251002 or equivalent in another qualifying study, may be enrolled in Protocol C0251008. The treatment duration of OLE study participation will be up to 48 weeks (treatment period is up through and including Week 52), with a 16 week follow up period. See Figure 1 for the study schematic.*

*Qualified participants will be randomized to receive open-label PF-06823859 600 mg IV every 4 weeks for up to 48 weeks, however the treatment period is up to Week 52. All participants will be followed for another 16 weeks in the Follow-up Period. Participants who are discontinued from study intervention will also enter the follow-up period.*

**Figure 1. Study Schema**

### **3. ENDPOINTS AND BASELINE VARIABLES: DEFINITIONS AND CONVENTIONS**

For the skin cohort (ie, participants entering C0251008 from Amended Stage 2 of C0251002), the major efficacy analyses assess changes in the modified CDASI *activity* and *damage* scores. The details of the calculation of these scores are presented in [Section 9.2](#).

For the muscle cohort (ie, participants entering C0251008 from Stage 3 of C0251002), the major efficacy analyses assess changes in the modified CDASI activity and damage scores and changes in the TIS and the CSM. The details of the calculation of the TIS are presented in [Section 9.3](#).

Safety assessments for the primary endpoint will be reported for all participants and by cohort. Efficacy assessments will generally be reported by cohort.

Unless specifically stated otherwise, the baseline value for all assessments is defined as the last non-missing measurement collected prior to the first administration of study drug at Day 1. Change from baseline is defined as the value at a specific visit minus the value from baseline.

#### **3.1. Primary Endpoint(s)**

##### **3.1.1. Incidence of Adverse Events (AEs)**

Reporting for AEs is described in [Section 6.6.1](#). Appendix 3 of the C0251008 Study Protocol provides definitions for an AE and SAE. An AE is considered treatment emergent relative to a given treatment if:

- the event occurs for the first time during the effective duration of treatment and was not seen prior to the start of treatment (for example, during the baseline or run-in period), or
- the event was seen prior to the start of treatment but increased in severity during treatment.

##### **3.1.2. Laboratory Abnormalities**

Reporting for laboratory data is described in [Section 6.6.2](#). To determine if there are any clinically significant laboratory abnormalities, the safety laboratory tests will be assessed against the criteria specified in the C0251008 Study Protocol. Baseline of safety laboratory tests will be the last pre-dose measurement.

### **3.1.3. Changes in Vital Signs**

Vital signs (including blood pressure, pulse, respiratory rates and temperature) will be measured after 5 minutes of rest as indicated in the Schedule of Activities. Baseline will be the last measurement prior to receiving study treatment. Reporting for changes in vital signs is described in [Section 6.6.3](#).

### **3.1.4. ECG Findings**

Reporting for ECG findings is described in [Section 6.6.4](#). Baseline will be the last measurement prior to receiving study treatment.

## **3.2. Secondary Endpoint(s)**

### **3.2.1. CDASI Activity and Damage Scores**

The CDASI activity and damage scores are continuous measures with ranges of 0-100 and 0-32 respectively, where higher scores indicate higher levels of disability. Both CDASI scores are computed as the sum of component scores as described in [Appendix 9.2](#). The absolute value and change from baseline (CFB) values of the CDASI activity and damage scores will be assessed.

### **3.2.2. TIS**

The TIS is a continuous measure ranging from 0 to 100 that assesses disease activity relative to baseline. By definition, all participants have a TIS of 0 at baseline. A TIS  $\geq 20$  represents minimal improvement, TIS  $\geq 40$  represents moderate improvement, and TIS  $\geq 60$  represents major improvement.

Six CSMs contribute to the TIS, including the PhGA, PtGA, MMT-8, HAQ-DI, global extramuscular disease activity assessment from the MDAAT, and muscle enzymes. The TIS is the sum of all 6 improvement scores associated with the change in each CSM.

[Appendix 9.3](#) provides full details on the computation of the TIS and each CSM. The absolute values and CFB in each CSM will be assessed.

#### **3.2.2.1. PhGA**

Physician Global Assessment Score (PhGA) is defined as a value within (0-100 mm or 0-10 cm) on a visual analog scale. For computation of the TIS, the PhGA is drawn from the MDAAT. Higher scores indicate a higher level of disability.

#### **3.2.2.2. PtGA**

Patient Global Assessment Score (PtGA) is defined as a value within (0-100 mm or 0-10 cm) on a visual analog scale. Higher scores indicate a higher level of disability.

### 3.2.2.3. MMT-8

MMT-8 is a tool that assesses muscle strength using manual muscle testing. Eight designated muscles are tested unilaterally with a total potential summed score of 0-80. Lower scores indicate a higher level of disability.

### 3.2.2.4. HAQ-DI

The HAQ-DI contains eight sections (including dressing & grooming, arising, eating, walking, hygiene, grip, reach, and activities) with items that can be scored from 0 to 3. Higher scores indicate higher level of disability. The HAQ-DI score used in the CSM calculation for the TIS is the average of these scores.

### 3.2.2.5. Global Extramuscular Disease Activity Assessment from the MDAAT

The global extramuscular disease activity assessment from the MDAAT is one of the CSMs used in the computation of the TIS. The global extramuscular disease activity is defined as a value within 0-10 cm on a visual analog scale. Higher scores indicate higher level of disability.

### 3.2.2.6. Muscle Enzymes

Five muscle enzymes are assessed for the TIS, including aldolase, alanine aminotransferase, aspartate aminotransferase, lactate dehydrogenase, and creatine kinase. The most abnormal serum muscle enzyme among these is used in the computation of the muscle enzyme CSM of the TIS.

## 3.3. Other Endpoint(s)

### 3.3.1. PK and PD Endpoints

The PK/PD endpoints include:

- Plasma PF-06823859 concentrations.
- PD biomarkers: total IFN $\beta$ , hsCRP, muscle biomarkers described in [Section 3.2.2.6](#).

The absolute value and CFB will be assessed for each biomarker.

### 3.3.2. Immunogenicity

Immunogenicity will be assessed through reporting the incidence of anti-drug antibodies (ADAs) and neutralizing antibodies (NAbs).

### 3.3.3. Columbia-Suicide Severity Rating Scale (C-SSRS)

The C-SSRS is used to assess suicidal ideation and behavior during the conduct of the study. The C-SSRS is a patient-reported questionnaire administered by the investigator or site staff that have been trained to administer the test. The absolute value and CFB in the C-SSRS will be assessed.

### 3.3.4. PROs

- European Quality of Life – 5 Dimensions-5 Level (EQ-5D-5L) Questionnaire assesses impact on health-related quality of life in 5 domains: mobility, self-care, usual activities, pain/discomfort, and anxiety/depression. Additionally, scores from the 5 domains may be used to calculate a single index value, also known as a utility score. Higher scores indicate higher level of disability. The absolute value and CFB in the EQ-5D-5L will be assessed.
- The SF-36 v.2 (Acute version) is a 36-item generic health status measure. It measures 8 general health concepts or domains: physical functioning (PF), role physical (RP), bodily pain (BP), general health (GH), vitality (VT), social functioning (SF), role emotional (RE) and mental health (MH). These domains are also summarized as physical and mental component scores (PCS and MCS). Higher scores indicate lower level of disability. The absolute value and CFB in the SF-36 v.2 scores will be assessed.

### 3.4. Baseline Variables

Unless specifically stated otherwise, the baseline value for all assessments is defined as the last non-missing measurement collected prior to the first administration of study drug at Day 1. *References to “baseline” in this study correspond to the Week 24 visit of the Phase 2 C0251002 study and Day 1 of this study.*

### 3.5. Safety Endpoints

Safety endpoints are described in [Section 3.1](#).

## 4. ANALYSIS SETS (POPULATIONS FOR ANALYSIS)

Data for all participants will be assessed to determine if participants meet the criteria for inclusion in each analysis population prior to releasing the database and classifications will be documented per standard operating procedures.

Participant Analysis Set	Description
Randomized	"Randomized" means a participant's agreement to participate in a clinical study following completion of the informed consent process. A participant will be considered enrolled if the informed consent is not withdrawn prior to participating in any study activity.
Full Analysis Set (FAS)	All participants enrolled who take at least 1 dose of study intervention.
Safety Analysis Set	All participants enrolled who take at least 1 dose of study intervention. This includes all such participants regardless of which parent study or stage the participant entered from.
Skin Safety Analysis Set	All participants with skin predominant DM who take at least 1 dose of study intervention including participants entering from Amended Stage 2 of the C0251002 protocol.
Muscle Safety Analysis Set	All participants with muscle predominant DM who take at least 1 dose of study intervention including participants entering from Stage 3 of the C0251002 protocol.
PK Concentration Set	All participants assigned to investigational study treatment and who take at least 1 dose of investigational product and have at least 1 measurable concentration.
PD Data Set	All participants assigned to investigational study treatment and who take at least 1 dose of investigational product and have at least 1 of the PD parameters of interest.
Immunogenicity assessment population	All enrolled subjects who received at least one dose of PF-06823859 with at least one post-treatment anti-PF-06823859 antibody determination.

Defined Analysis Set (Efficacy)	Description
Skin Analysis Set	All participants with skin predominant DM in the FAS including participants who were enrolled in Amended Stage 2 of the C0251002 study.
Muscle Analysis Set	All participants with muscle predominant DM in the FAS including participants who were enrolled in Stage 3 of the C0251002 study.

Pooled Skin Analysis Set	All participants in the FAS with a CDASI activity score of 14 or greater at baseline of study C0251002. This analysis set includes all subjects from Amended Stage 2 of the C0251002 study and potentially some subjects from Stage 3 of the C0251002 study who also have skin disease.
---------------------------------	--

## 5. GENERAL METHODOLOGY AND CONVENTIONS

Final analyses will occur after database lock after Last Participant Last Visit (LPLV).

### 5.1. Hypotheses and Decision Rules

No statistical hypothesis testing is planned for this study.

### 5.2. General Methods

Analyses will generally be reported by cohort (skin or muscle). Sensitivity analyses will be performed for the CDASI activity score, CDASI damage score, and TIS. Supportive analyses for the CDASI activity and damage scores will use the pooled skin analysis set, which includes all participants from Amended Stage 2 of study C0251002 and participants from Stage 3 of study C0251002 with sufficient skin disease (see [Section 4](#)).

#### 5.2.1. Analyses for Continuous Endpoints

For E1 and E2, the Longitudinal ANCOVA Model (LANCOVA, used for secondary analyses) and conventional analysis of covariance (ANCOVA, used for sensitivity analyses) methods will be used.

The LANCOVA analysis will use either the change from baseline value (CDASI activity or CDASI damage) or the direct value (TIS) as the continuous variable in the outcome in the model, which will be fit from baseline to Week 52. For the CFB CDASI activity and damage endpoints, the LANCOVA models will include week as a fixed effect and baseline value as a covariate. For the TIS, the LANCOVA model will include week as a fixed effect. In all models, an unstructured variance-covariance matrix will be used. Estimates and 90% CI will be reported. No p-values will be computed for the analysis.

### 5.3. Methods to Manage Missing Data

- In the longitudinal modeling (LANCOVA) of repeated measures of continuous outcomes (both efficacy measures and covariates) it is assumed that missing data are generated by the “missing at random” mechanism and, therefore imputation of the missing data is not necessary.
- In all data presentations of PK outcome (except listings), concentrations below the limit of quantification (BLQ) will be set to zero. (In listings BLQ values will be reported as “<LLQ”, where LLQ will be replaced with the value for the lower limit of

quantification). In summary tables and plots of median profiles, statistics will be calculated having set concentrations to missing if concentration measurement was not done or sample was not collected.

- The PK summary statistics will not be presented at a particular time point if more than 50% of the PK data are missing.
- Immunogenicity assay titers will be used to determine incidence for ADA and NAb. If a titer value is missing data imputation will not occur and missing values will be represented by NC (ie, not-calculated).
- For other endpoints, statistical analyses will be based on available data. Missing data will not be imputed.

## 6. ANALYSES AND SUMMARIES

### 6.1. Primary Endpoint(s)

#### 6.1.1. Incidence of AEs, Laboratory Abnormalities, Changes in Vital Signs, and ECG Findings

- Estimand strategy: Not applicable for safety endpoints.
- Analysis sets: Safety Analysis Set, Skin Safety Analysis Set, Muscle Safety Analysis Set.
- Analysis methodology: Descriptive statistics.
- Intercurrent events and missing data: Data after study withdrawal will be excluded; intermediate missing values will not be imputed.
- Categorical outcomes (eg, AEs) will be summarized by participant counts and percentage. Continuous outcome (eg, BP, heart rate) will be summarized using N, mean, median, standard deviation, minimum, maximum. Change from baseline in laboratory data and vital signs will also be summarized according to sponsor Data Standards.

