7.3. Lost to Follow-Up

A participant will be considered lost to follow-up if he or she repeatedly fails to return for scheduled visits and is unable to be contacted by the study site.

The following actions must be taken if a participant fails to attend a required study visit:

- The site must attempt to contact the participant and reschedule the missed visit as soon as possible. Counsel the participant on the importance of maintaining the assigned visit schedule, and ascertain whether the participant wishes to and/or should continue in the study;
- Before a participant is deemed lost to follow-up, the investigator or designee must make every effort to regain contact with the participant (where possible, 3 telephone calls and, if necessary, a certified letter to the participant's last known mailing address or local equivalent methods). These contact attempts should be documented in the participant's medical record;
- Should the participant continue to be unreachable, he/she will be considered to have withdrawn from the study.

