8.3.1. Time Period and Frequency for Collecting AE and SAE Information

The time period for actively eliciting and collecting AEs and SAEs (“active collection period”) for each participant begins from the time the participant provides informed consent, which is obtained before the participant’s participation in the study (ie, before undergoing any study-related procedure and/or receiving study intervention), through and including a minimum of 5 months after the last administration of the study intervention.

Since this is an extension study, once the ICD is signed, any newly developed adverse events recorded prior to study drug dosing should be recorded in the participant’s medical history. Once the participant receives study drug, all and any adverse events will be reviewed and recorded on the adverse event page.

Follow-up by the investigator continues throughout and after the active collection period and until the AE or SAE or its sequelae resolve or stabilize at a level acceptable to the investigator.

For participants who are screen failures, the active collection period ends when screen failure status is determined.

If the participant withdraws from the study and also withdraws consent for the collection of future information, the active collection period ends when consent is withdrawn.

If a participant permanently discontinues or temporarily discontinues study intervention because of an AE or SAE, the AE or SAE must be recorded on the CRF and the SAE reported using the CT SAE Report Form.

Investigators are not obligated to actively seek information on AEs or SAEs after the participant has concluded study participation. However, if the investigator learns of any SAE, including a death, at any time after a participant has completed the study, and he/she considers the event to be reasonably related to the study intervention, the investigator must promptly report the SAE to Pfizer using the CT SAE Report Form.

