### 2.1. Study Objectives, Endpoints, and Estimands

**Table 2. List of Study Objectives, Estimands, and Endpoints**

Objectives	Endpoints	Estimands
Primary:	Primary:	Primary:

 
To evaluate the long-term safety and tolerability of PF-06823859.
 
	
 
Incidence of AEs, laboratory abnormalities, changes in vital signs, and ECG findings.
 
	
 
There are no defined estimands for safety and tolerability endpoints; these will be analyzed using Pfizer data standards, as applicable.
 

Secondary:	Secondary:	Secondary:

 
To evaluate the long-term efficacy of PF-06823859 in adult participants with moderate to severe DM.
 
	
 
Change from baseline in CDASI activity score at Week 52.
 
	
 
E1: This estimand uses a hypothetical estimand strategy (ICH E9 addendum) estimating the mean effect of PF-06823859 in the absence of intercurrent events (study withdrawal). This is the mean change from baseline to Week 52 CDASI activity score for all randomized and dosed participants with non-missing baseline score in the (a) Skin Analysis Set and (b) Muscle
 

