#### 6.1.1.1. Sensitivity/Supplementary Analyses

### 6.2. Secondary Endpoint(s)

#### 6.2.1. CDASI Activity and Damage Scores

##### 6.2.1.1. Main Analysis

- Estimand strategy: E1.

- Analysis sets: Skin Analysis Set and Muscle Analysis Set.
- Analysis methodology: Each CDASI endpoint (including CFB CDASI activity score, CFB CDASI damage score, absolute value of CDASI activity score, and absolute value of CDASI damage score) will be analyzed using LANCOVA including data from baseline to Week 52 with week as a fixed effect and baseline score as a covariate and an unstructured covariance matrix ([Section 5.2.1](#)).
- Intercurrent events and missing data: Data after study drug discontinuation will be excluded; intermediate missing values will not be imputed.
- The sample size, mean, standard deviation, median, minimum, and maximum at the baseline and postbaseline visits for observed CDASI scores and change from baseline CDASI scores will be presented for each cohort for each CDASI endpoint.
- For each CDASI endpoint, the least-squares (LS) means and the 90% confidence interval for the LS means will be presented and plotted for all postbaseline visits.

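### SAP 6.1.1 drops safety data recorded after study withdrawal from the primary endpoint, in conflict with the protocol's AE collection period and with SAP 2.1.1

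*SAP*

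**What the plan says.** SAP 6.1.1 covers the whole primary endpoint: AEs, laboratory abnormalities, vital signs and ECG findings. It marks the estimand strategy as not applicable, then gives this rule for intercurrent events and missing data: "Data after study withdrawal will be excluded; intermediate missing values will not be imputed". SAEs and deaths are not carved out.

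Protocol 8.3.1 runs active AE and SAE collection from consent "through and including a minimum of 5 months after the last administration of the study intervention". Study withdrawal shortens this period only where the participant "withdraws from the study and also withdraws consent for the collection of future information, the active collection period ends when consent is withdrawn". Protocol 7.2 lists refusal of further procedures and loss to follow-up as reasons for leaving the study. On the second, Protocol 7.3 says: "Should the participant continue to be unreachable, he/she will be considered to have withdrawn from the study".

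SAP 2.1.1, like Protocol 9.1.1.1, says that all safety data are summarised for everyone who receives at least one dose. SAP 6.6 says that safety is monitored over both the treatment and follow-up periods.

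The efficacy sections use a different cut-off. SAP 6.2.1.1 says: "Data after study drug discontinuation will be excluded; intermediate missing values will not be imputed".

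**The concern.** Two exits from the study leave the collection period open: refusing further procedures, and becoming unreachable. An SAE or death that the site learns of afterwards is within Protocol 8.3.1 and belongs in the database, yet SAP 6.1.1 removes it from the primary tables. Nothing in either document justifies discarding collected safety data, and the rule contradicts the SAP's own undertaking in 2.1.1.

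Safety is the primary objective, there is no control arm, and about 30 participants are expected, so single events are visible in the reported incidences. The incidence denominator is every dosed participant. Removing a recorded event can therefore lower an incidence or leave it unchanged, but never raise it.

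The key term is also unsettled. SAP Table 2 defines the efficacy estimands "in the absence of intercurrent events (study withdrawal" (the bracket closes there). SAP 2.1.2 then applies the same estimands as follows: "Measurements taken after a participant withdraws from treatment will be censored and treated as missing data". One label thus covers leaving the study in one place and stopping treatment in another, and SAP 6.1.1 uses that label without defining it.

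**Working it through.** The documents give no figure to reproduce: there is no hypothesis test, no power calculation and no stated withdrawal rate. The check is a comparison of the text, followed by arithmetic on size.

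**1. Which data the rule removes**

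| Situation | Protocol | Under SAP 6.1.1, read literally |
|---|---|---|
| Stops study drug, stays for follow-up | 7.1: not a study withdrawal; safety evaluation continues | Kept |
| Dies while in the study | 7.2: death is itself the reason for leaving | Kept; the death is the exit event |
| Leaves and withdraws consent for future information | 7.2 and 8.3.1: collection ends | Nothing further to exclude |
| Refuses further procedures or is lost to follow-up, consent for collection intact | 8.3.1: collection period still open | Recorded events excluded |

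Only the last row is a conflict.

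**2. How much of the five-month window is affected**

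- The last scheduled dose is at Week 48: Day 1 + 48 × 7 = Day 337. The final visit is at Week 68: Day 1 + 68 × 7 = Day 477. These match the target days in SAP 9.1.
- The gap is 477 − 337 = 140 days. Five months is about 150 to 153 days.
- For a completer, all but the last 10 to 13 days of the window falls before the final visit. That remainder comes after completion, not after withdrawal, so the rule does not touch it.

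**3. Effect of one affected participant**

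This assumes that the participant had no earlier event of the same kind. Intervals are exact (Clopper-Pearson) 95% intervals. N = 30 is the planned size; a cohort of 15 is an assumed split.

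| N | Event excluded | Event included | Shift |
|---|---|---|---|
| 30 | 0/30 = 0% (0 to 11.6%) | 1/30 = 3.3% (0.1 to 17.2%) | 3.3 points |
| 15 | 0/15 = 0% (0 to 21.8%) | 1/15 = 6.7% (0.2 to 31.9%) | 6.7 points |

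**4. How many participants might be affected**

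Let *d* be the proportion who withdraw but whose events can still be recorded, and *p* the chance that such a person has a recorded event afterwards. Both are assumptions. The expected number is 30 × *d* × *p*, and P(at least one) = 1 − (1 − *dp*)^30.

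| *d* | *p* | Expected | P(at least one) |
|---|---|---|---|
| 5% | 10% | 0.15 | 14.0% |
| 10% | 10% | 0.30 | 26.0% |
| 20% | 10% | 0.60 | 45.5% |

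With *p* from 2% to 30% over the same values of *d*, the expected number runs from 0.03 (*d* = 5%, *p* = 2%) to 1.8 (*d* = 20%, *p* = 30%).

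**The case against.** The strongest case against is that the rule hardly bites. Someone lost to follow-up is by definition unreachable, and Protocol 8.3.1 adds: "Investigators are not obligated to actively seek information on AEs or SAEs after the participant has concluded study participation". Scheduled laboratory, vital-sign and ECG measurements will mostly not exist after full withdrawal. What remains is the occasional late-reported AE, SAE or death. All of this stands, and it limits the size of the problem. It does not remove the conflict: not having to seek events is different from discarding those that are recorded.

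A reader might infer several stronger points that the documents do not support:

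- *The whole five-month window is lost.* Most events in it come from participants still in the study and are kept.
- *All follow-up data of treatment discontinuers are lost, up to 16 weeks each.* Protocol 7.1 separates stopping drug from leaving the study, and SAP 6.6 includes follow-up. The loose wording sits in the efficacy estimands, which SAP 6.1.1 says do not apply to safety. It is a reason to define the term, not evidence that these data are excluded.
- *The safety rule copies the efficacy rule.* The two cut-offs differ, and the safety one comes later.
- *Withdrawal is driven by toxicity, so the bias is large.* Neither document says so. The protocol routes adverse events and flares to treatment discontinuation with continued follow-up, and those data are kept.
- *Residual drug at a fixed time after the last dose measures the loss.* The excluded period starts whenever a participant withdraws, so no single figure describes it.

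It is also fair to say that changing one sentence does not fully settle the treatment-emergent AE tables. These depend on the effective duration of treatment in SAP 3.1.1, which the SAP does not define.

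**Conclusion.** The rule is wrong as written and should be changed, within a narrow scope. AEs, SAEs or deaths recorded after full study withdrawal, with consent for collection intact, would be left out of the primary summaries. That contradicts Protocol 8.3.1 and SAP 2.1.1. Deaths are affected only when learned of after an earlier withdrawal.

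For incidences the direction is certain, because the denominator is fixed. The size per case is 3.3 points at N = 30. The number of cases is probably small: 0.15 to 0.60 expected if 5% to 20% withdraw but remain reportable and 10% of those have an event. These rates are illustrative and have no source in the documents.

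The conclusion on discontinuers rests on reading study withdrawal as Protocol 7.1 does. If programming equated it with withdrawal from treatment, as the estimand text does, the loss would be wider. The SAP should close off that possibility.

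**What to change.** In SAP 6.1.1, replace the exclusion with a statement to this effect: all AEs, SAEs, deaths, laboratory, vital-sign and ECG data recorded from the first dose in this study to the end of the Protocol 8.3.1 collection period are included for every dosed participant, whatever the treatment or study status; the only data excluded are those that may not be used after withdrawal of consent. The rule of not imputing missing values can stay.

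Define study withdrawal once, as distinct from study drug discontinuation, and use the two terms consistently in SAP Table 2, 2.1.2 and 6.1.1. State how the effective duration of treatment in SAP 3.1.1 relates to the collection period, so that the treatment-emergent tables follow the same rule.

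The cost is SAP wording only. No extra data are collected, and the reported incidences may become slightly less favourable.
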